	
diagnosed with septic shock, fluid resuscitation should be performed according to the routine diagnosis and treatment. 4 The legal guardian has signed the informed consent.

	
excluded criteria:
 
1 combined with neurogenic shock, trauma and hemorrhagic shock; 2 symptomatic patent ductus arteriosus; 3 combined with congenital heart disease; 4 give up treatment or death within 24 hours of admission; 5 The legal guardian refused to participate in the study; 6 Key information and information missing.

Treatment plan	
This study was an observational study. Clinicians developed a diagnosis and treatment plan based on the treatment plan for neonatal sepsis in the sixth edition of " Practical Neonatology " and the " International Guidelines for the 2020 Saving Sepsis Campaign: Management of Septic Shock and Sepsis-related Organ Dysfunction in Children. "

efficacy evaluation	
The main efficacy indicators: hospitalization time and cumulative hospitalization time, mortality.
 
Secondary efficacy indicators: cumulative fluid volume during fluid resuscitation, use of vasoactive drugs and mechanical auxiliary gas.

	
Safety evaluation index: Mortality.

statistical method	
Measurement data and count data were expressed as mean \pm standard deviation [or median (interquartile range)] and percentage (%), respectively. Normal and non-normal distribution data were analyzed by two independent sample t test and Mann-Whitney U test, respectively. The chi-square test was used to compare the count data rates between groups. Kaplan-Meier

	
method was used to draw the survival curve, and Log-rank test was used to compare the difference of 28-day cumulative survival rate between the two groups. Baseline covariates were adjusted in the Cox proportional hazards model to calculate the hazard ratios (HRs) and their 95 % confidence intervals. Logarithmic conversion was performed on hospital stay and organ support time and linear regression analysis was used to calculate a 95 % confidence interval for reporting. No data with missing information is interpolated. The above statistical analysis was performed using R software, and the test was bilateral, and $p < 0.05$ was considered statistically significant.

Research period
	
January 1, 2022 – December 31, 2023

一、 Research background

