In this study, children with neonatal septic shock diagnosed in the neonatal intensive care unit of the Second People 's Hospital of Guangdong Province from January 1,2022 to December 31,2023 were included. According to the different monitoring methods used in routine / clinical shock treatment, 30 cases of severe ultrasound-assisted fluid resuscitation, 30 cases of NICOM-assisted fluid resuscitation and 30 cases of routine fluid resuscitation were collected. The demographic data, blood examination and microbiological examination data of the three groups at admission were collected. The fluid volume, blood lactic acid, blood pressure, vasoactive drugs (such as dopamine and epinephrine / norepinephrine), mechanical ventilation, renal replacement therapy and antibiotic use before fluid resuscitation were collected. The cumulative fluid infusion volume during fluid resuscitation (6 hours), and the use of vasoactive drugs and mechanical ventilation for 6 hours were collected. NICU hospitalization time, cumulative hospitalization time and mortality were collected.

四、 case selection

1. Inclusion criteria:

1 Born less than 28 days on admission; 2 Conform to the diagnostic criteria for neonatal septic shock in the ' 2020 International Guidelines for Saving Sepsis Campaign: Management of Septic Shock and Sepsis-related Organ Dysfunction in Children; 3 For children diagnosed with septic shock, fluid resuscitation should be performed according to the routine diagnosis and treatment. 4 The legal guardian has signed the informed consent.

2. excluded criteria:

1 combined with neurogenic shock, trauma and hemorrhagic shock; 2 symptomatic patent ductus arteriosus; 3 combined with congenital heart disease; 4 give up treatment or death within 24 hours of admission; 5 The legal guardian refused to participate in the study; 6 Key information and information missing.

3. Elimination criteria

Subjects who have been enrolled in the study but meet one of the following criteria should be excluded :

(1) After inclusion, those who did not meet the inclusion criteria or met the exclusion criteria were found.

(2) Those who have not used test drugs / interventions.

4. Standard for suspension of research

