(1) If the following conditions occur during the experiment : cardiac arrest, intestinal perforation, intracranial and other serious complications ; (2) the need for rescue is not suitable for experimental related operators ; (3) The competent physician believes that the clinical condition is not suitable for continuing the experiment ; (4) If the clinical symptoms and other auxiliary examinations are inconsistent with the relevant non-invasive examination results ; (5) Parents did not agree to continue the experiment during the experiment.

4. Drop-out / exit criteria

Expulsion / withdrawal criteria : (1) the competent physician believes that the clinical condition is not suitable for the continuation of the experiment ; (2) If the clinical symptoms and other auxiliary examinations are inconsistent with the relevant non-invasive examination results ; (3) Parents did not agree to continue the experiment during the experiment.

五、 research method

In this study, children with neonatal septic shock diagnosed in the neonatal intensive care unit of the Second People 's Hospital of Guangdong Province from January 1,2022 to December 31,2023 were included. According to the different monitoring methods used in routine / clinical shock treatment, 30 cases of severe ultrasound-assisted fluid resuscitation, 30 cases of NICOM-assisted fluid resuscitation and 30 cases of routine fluid resuscitation were collected. The demographic data, blood examination and microbiological examination data of the three groups at admission were collected. The fluid volume, blood lactic acid, blood pressure, vasoactive drugs (such as dopamine and epinephrine / norepinephrine),

mechanical ventilation, renal replacement therapy and antibiotic use before fluid resuscitation were collected. The cumulative fluid infusion volume during fluid resuscitation (6 hours), and the use of vasoactive drugs and mechanical ventilation for 6 hours were collected. NICU hospitalization time, cumulative hospitalization time and mortality were collected.

六、 Observation items and detection time points

(1) The demographic data, blood examination and microbiological examination data of the three groups at admission were collected.

(2) The fluid volume, blood lactic acid, blood pressure, vasoactive drugs (such as dopamine and adrenaline / norepinephrine), mechanical ventilation, renal replacement therapy and antibiotic use before fluid resuscitation were collected.

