(3) The cumulative fluid infusion volume during fluid resuscitation (6 hours), and the use of vasoactive drugs and mechanical ventilation for 6 hours were collected.

(4) NICU hospitalization time, cumulative hospitalization time and mortality were collected.

七、 standards for efficacy appraisal

The main efficacy criteria : NICU hospitalization time and cumulative hospitalization time, mortality.

Secondary efficacy criteria : cumulative fluid volume during fluid resuscitation (6 hours), and use of vasoactive drugs and mechanical ventilation for 6 hours.

八、 Observation of adverse events

Observation of adverse events : Clinicians should evaluate the fluid resuscitation of children at any time during the experiment. If the clinical symptoms and other auxiliary examinations (such as heart rate, liver size, mental state, X-ray, blood gas analysis, etc.) are

inconsistent with the relevant non-invasive examinations, the experiment should be terminated immediately and the superior physician should be found in time to assist.

九、 Data security monitoring

Clinical research will develop a corresponding data security monitoring plan based on the size of the risk. All adverse events were recorded in detail, properly handled and tracked until they were properly resolved or stable. Serious adverse events and unexpected events were reported to the ethics committee, competent authorities, sponsors and drug supervision and management departments in a timely manner according to the regulations. The main researchers regularly conduct a cumulative review of all adverse events, and if necessary, convene a meeting of researchers to assess the risks and benefits of the study ; research that is greater than the minimum risk will arrange independent data monitors to monitor the research data, and high-risk research will establish an independent data security supervisory committee to monitor the accumulated security data and effectiveness data to make recommendations on whether the research will continue.

十、 Statistical processing

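### Suspension and withdrawal rules are triggered by deterioration after enrolment, and nothing keeps those infants in the mortality and stay analyses.

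*Combined protocol and SAP*

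**What the plan says.** Section 四 (case selection) has three lists that act after enrolment.

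- **Elimination criteria.** Enrolled infants later found to fail an inclusion criterion or to meet an exclusion criterion are to be excluded, as are those who did not receive the test drug or intervention. Exclusion criterion 6 is missing key information.
- **Suspension**, headed "Standard for suspension of research". Item (1) reads "If the following conditions occur during the experiment : cardiac arrest, intestinal perforation, intracranial and other serious complications". Item (2) is garbled: "the need for rescue is not suitable for experimental related operators". Item (3) is "The competent physician believes that the clinical condition is not suitable for continuing the experiment". Items (4) and (5) are disagreement with the non-invasive examination and parental refusal to continue.
- **Drop-out / exit.** It opens "Expulsion / withdrawal criteria : (1) the competent physician believes that the clinical condition is not suitable for the continuation of the experiment" and then repeats suspension items (4) and (5). Suspension items (1) and (2) are not in it.

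The Abstract states "This study was an observational study". Section 七 states "The main efficacy criteria : NICU hospitalization time and cumulative hospitalization time, mortality", and the Abstract names mortality as the safety index. Section 十 plans Kaplan-Meier curves, a log-rank test of 28-day survival, a Cox model and regression of log-transformed stay, with no imputation. It defines no analysis set and no censoring rule.

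**The concern.** Arrest, perforation, intracranial complications and a physician's judgement that an infant cannot continue all arise after enrolment, and they plausibly precede death. Death is both a main outcome and the safety index. A rule that ends participation on such events, without securing follow-up, selects on the outcome being compared.

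Three things are at stake. If the infants removed die more often than the others, mortality would be underestimated. Physician judgement is one of the triggers and no blinding is described, so removal could differ between the ultrasound, NICOM and conventional groups and create or hide a difference. Stay would be compared among a selected remainder of infants, with a bias whose direction cannot be predicted.

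**Working it through.** The plan states no figure on this point to reproduce. The 90 cases (30 per group) come with no power, effect size or dropout assumption.

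**Step 1: how an infant can leave the analysis.**

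| Trigger | Suspension list | Withdrawal list | Effect on follow-up and analysis |
|---|---|---|---|
| Arrest, perforation, intracranial or other serious complication | item (1) | absent | not stated |
| Item on rescue (garbled) | item (2) | absent | not stated |
| Physician judges condition unsuitable | item (3) | item (1) | withdrawal; later follow-up not stated |

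For the physician's judgement, the route out is explicit. For the first two rows it is open: if suspension stops data collection, key information will be missing. Missing key information is exclusion criterion 6, elimination criterion (1) lets an exclusion criterion be applied after enrolment, and nothing is imputed. If such infants are instead censored at suspension in the survival analysis, the censoring is likely to be informative.

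**Step 2: illustration of size.** Inputs:
- n = 30 per group (Abstract).
- True mortality m = 40%. This is an assumption; section 一 quotes in-hospital mortality above 40% as background.
- Share of the group dropped, s, and mortality among those dropped, q. The documents give neither, so ranges are shown.

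Observed mortality = (m − s·q) / (1 − s).

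| s (infants dropped) | q = 60% | q = 80% | q = 100% |
|---|---|---|---|
| 10% (3) | 37.8% | 35.6% | 33.3% |
| 20% (6) | 35.0% | 30.0% | 25.0% |
| 30% (9) | 31.4% | 22.9% | 14.3% |

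Example: s = 20%, q = 80% gives (0.40 − 0.16) / 0.80 = 0.30.

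With m = 20% instead, s = 10% gives 15.6%, 13.3% and 11.1% across the same three values of q.

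**Step 3: unequal loss with no true difference.** Start from 12/30 deaths in each of two groups and remove deaths from one group only.

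| Deaths removed | Observed, against 12/30 (40%) | Chi-square p, uncorrected | Chi-square p, corrected | Fisher p |
|---|---|---|---|---|
| 3 | 9/27 = 33.3% | 0.60 | 0.81 | 0.78 |
| 6 | 6/24 = 25.0% | 0.25 | 0.38 | 0.38 |
| 9 | 3/21 = 14.3% | 0.047 | 0.095 | 0.064 |

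This is the extreme case, in which every infant removed dies and all removals fall in one group. A few removals shift the estimate. Nine are needed before the uncorrected test falls below 0.05, and at nine the corrected and exact tests do not.

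**The case against.** The strongest reply is that the documents never say suspended infants are removed. Elimination is a separate list, and neither it nor the drop-out list names arrest, perforation, intracranial complications or rescue. The contrast suggests that these events were not meant as withdrawal grounds. Mortality and stay are listed for collection without an exception for suspended infants, and section 九 has adverse events recorded and tracked until resolved or stable. What is suspended might be only the ultrasound or NICOM assistance, since the text mentions test interventions and experimental operators.

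Much of this stands. A reader might infer that every infant with an arrest or perforation leaves the analysis, or that the study stops collecting data on them. The text does not support either as a fact. It leaves the matter open, apart from the physician-judgement item, which is a stated withdrawal criterion. Tracking an event until it is stable does not secure 28-day vital status or length of stay, so the gap remains.

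A reader might also take the heading to mean that one triggering event halts the whole study. The content does not fit: the physician's view of the condition and parental refusal concern a single infant, and section 九 places continuation of the study with cumulative review, researcher meetings or a data committee.

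The size is uncertain. Some infants survive a triggering event, which is why the illustration varies q. The period meant by the word experiment is not defined; if it is the 6-hour resuscitation window, later events would not trigger the rule. Deaths within 24 hours of admission are already excluded by another criterion, and the 40% background figure does not describe 24-hour survivors.

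**Conclusion.** The concern holds in this form: section 四 ties suspension and withdrawal to deterioration after enrolment, and the plan does not keep the affected infants in follow-up or in the analysis. Removal is explicit for the physician-judgement item and possible by omission for the complications and the garbled rescue item.

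Underestimated mortality is conditional: it follows if suspended infants are dropped and die more often than the others. With assumed true mortality of 40%, the illustrated shortfall runs from about 2 percentage points (40.0 − 37.8 = 2.2) to about 26 (40.0 − 14.3 = 25.7). Suspension rates and mortality among suspended infants are assumptions throughout. The direction of any between-group bias cannot be known from the documents.

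This should be fixed before enrolment, because it touches every main outcome and vital status or stay left uncollected may not be recoverable.

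**What to change.** Add one paragraph to section 四, with a matching sentence in section 十:

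- The lists apply to the individual infant. Suspension or physician-decided withdrawal does not end outcome follow-up.
- Every enrolled infant stays in the original monitoring group, with vital status to day 28, NICU stay and total stay recorded and analysed.
- Only a guardian's withdrawal of consent ends data collection.
- No infant is excluded or censored because of suspension, and the missing-information criterion is not applied to data lost through suspension.
- Suspensions and withdrawals are reported by group and reason.

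The suspension and withdrawal lists must also be reconciled, and item (2) reworded so that its meaning is clear. Which clinical events stop study procedures is left to the investigators.

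The cost is slightly more data collection from routine records. No extra patients or procedures are needed, and no new sample size follows. In the illustration, each group would keep its 30 infants and its 12/30 deaths.

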Clinical research protocol

Project name: Application of severe ultrasound in fluid resuscitation of neonatal septic shock

leading unit: Guangdong Second Provincial General Hospital

project leader: [name]

Department: Pediatrics

Research period: January 1,2022 to December 31,2023

NCT No.: none.

Version No.: V3.0

Version Date: November 29, 2021

Abstract

object name	Lung ultrasound-guided fluid resuscitation in neonatal septic shock
goal of study	In this study, a prospective observational study was conducted to compare the effects of severe ultrasound-assisted fluid resuscitation and conventional fluid resuscitation on the prognosis of children with neonatal septic shock, so as to evaluate the application value of the two techniques in fluid resuscitation of neonatal septic shock.
research design	
n this study, children with neonatal septic shock diagnosed in the neonatal intensive care unit of the Second People 's Hospital of Guangdong Province from January 1,2022 to December 31,2023 were included in the population. According to the different monitoring methods used in conventional / clinical shock treatment, 30 cases of fluid resuscitation assisted by severe ultrasound, 30 cases of fluid resuscitation assisted by NICOM and 30 cases of conventional fluid resuscitation were collected, a total of 90 cases.
 
(1) The demographic data, blood examination and microbiological examination data of the two groups at admission were collected.
 
(2) The fluid volume, blood lactic acid, blood pressure, vasoactive drugs (such as dopamine and epinephrine / norepinephrine), mechanical ventilation, renal replacement therapy and antibiotic use were collected before fluid resuscitation.
 
(3) The cumulative fluid infusion volume during fluid resuscitation (6 hours), and the use of vasoactive drugs and mechanical ventilation for 6 hours were collected.
 
(4) NICU hospitalization time, cumulative hospitalization time and mortality were collected.

Total number of cases studied	90 cases (30 cases in each group)
case selection	
Inclusion criteria:
 
1 Born less than 28 days on admission; 2 Conform to the diagnostic criteria for neonatal septic shock in the ' 2020 International Guidelines for Saving Sepsis Campaign: Management of Septic Shock and Sepsis-related Organ Dysfunction in Children; 3 For children

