excessive lung water volume load should be considered. Increases should begin to make adjustments in fluid therapy and respiratory therapy that are most suitable for patients [28]. However, previous studies are basically aimed at adults, and the number of studies in neonates is very limited. In clinical studies, due to the particularity of neonatal anatomy and physiology, there is a lack of research on the application of severe ultrasound technology in fluid resuscitation of neonatal septic shock. [29] There is an urgent need for an effective non-invasive monitoring method to assist fluid resuscitation in children with septic shock.

At present, the fluid resuscitation methods used in our department for neonates with septic shock mainly include : conventional fluid resuscitation, severe ultrasound-guided fluid resuscitation and NICOM-assisted fluid resuscitation. In this prospective observational study, children with neonatal septic shock diagnosed in the neonatal intensive care unit of Guangdong Second People 's Hospital from January 1,2022 to December 31,2023 were included in the study. According to the different monitoring methods used in shock treatment, 30 cases of severe ultrasound-assisted fluid resuscitation, 30 cases of NICOM-assisted fluid resuscitation and 30 cases of conventional fluid resuscitation were collected, a total of 90 cases. The hemodynamic differences, NICU hospitalization time, renal replacement therapy / mechanical ventilation, and 28-day mortality were compared among the three groups to comprehensively evaluate the application value of cardiopulmonary ultrasound and non-invasive cardiac output in fluid resuscitation of neonatal septic shock. Improve the therapeutic effect of neonatal septic shock, enrich the application field of clinical ultrasound, and promote the cross-fusion of ultrasound and pediatrics, and provide clinical basis for subsequent prospective studies.

二、 research objective

1. Main Objective: To study the application value of severe ultrasound and non-invasive cardiac output technique in fluid resuscitation of neonatal septic shock.

2.Secondary purpose: To promote the therapeutic effect of neonatal septic shock and enrich the application field of clinical ultrasound technology.

三、 Research Design Types, Principles, and Test Procedures

1. Research Design

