Measurement data and count data were expressed as mean \pm standard deviation [or median (interquartile range)] and percentage (%), respectively. Normal and non-normal distribution data were analyzed by two independent sample t test and Mann-Whitney U test, respectively. The chi-square test was used to compare the count data rates between groups. Kaplan-Meier method was used to draw the survival curve, and Log-rank test was used to compare the difference of 28-day cumulative survival rate between the two groups. Baseline covariates were adjusted in the Cox proportional hazards model to calculate the hazard ratios (HRs) and their 95 % confidence intervals. Logarithmic conversion was performed on hospital stay and organ support time and linear regression analysis was used to calculate a 95 % confidence interval for reporting. No data with missing information is interpolated. The above statistical analysis was performed using R software, and the test was bilateral, and $p < 0.05$ was considered statistically significant.

十一、 Ethics in clinical research

Clinical research will follow the World Medical Congress ' Helsinki Declaration ' and other relevant provisions. Before the study began, the clinical study was carried out after the ethics committee approved the test plan. Before each subject is selected for this study, the researcher has the responsibility to fully and comprehensively introduce the purpose, procedure and possible risks of this study to the subjects or their agents, and to sign a written informed consent form. The subjects should be informed that they have the right to withdraw from the study at any time. Informed consent should be retained as a clinical research document for review. The personal privacy and data confidentiality of the subjects will be protected during the study.

十二、 Research progress

January 1, 2022 - March 31, 2022 : Pre-project preparation, harmonization of data collection standards, training of personnel

From April 1,2022 to May 31,2023 : the specific implementation stage of the experiment, case data were collected.

From June 1,2023 to December 31,2023 : Write scientific research papers and project summary reports 1 Organize research data and conduct statistical analysis ; 2 writing and submission of scientific research papers ; 3 Summarize the research results and write the project summary report.

十四、 reference

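### The plan sets no common time zero: early deaths are excluded by time from admission, and stay and 28-day survival have no stated origin, although the exposure starts at fluid resuscitation

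*Combined protocol and SAP*

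**What the plan says.** - **Exposure.** Sections 三 and 五 form the groups by the monitoring method used in treating shock, so the comparison begins when fluid resuscitation begins.
- **Eligibility.** Section 四.1 sets an age limit, "Born less than 28 days on admission", and requires septic shock. The shock must be diagnosed in the NICU, but nothing limits the time from admission to shock.
- **Early deaths.** Section 四.2 (and the Abstract) excludes infants with "give up treatment or death within 24 hours of admission". Elimination criterion (1) in Section 四.3 applies the exclusions after enrolment as well.
- **Baseline data.** Section 六 item (1): "The demographic data, blood examination and microbiological examination data of the three groups at admission were collected". Item (2) is different: prior fluid volume, lactate, blood pressure, vasoactive drugs, ventilation, renal replacement and antibiotics are recorded before resuscitation.
- **Outcomes.** Section 七: "The main efficacy criteria : NICU hospitalization time and cumulative hospitalization time, mortality". No start or end of stay is defined. The 6-hour secondary outcomes are tied to resuscitation.
- **Analysis.** Section 十 uses log-transformed stay in linear regression, and Kaplan-Meier, log-rank and Cox methods for 28-day survival. It states no time origin. The interval from admission to shock is neither a listed data item nor a named covariate.

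**The concern.** Time before resuscitation cannot be affected by how resuscitation is monitored. If stay is counted from admission, as the term is ordinarily used, those days enter a primary outcome. They pull a true ratio towards 1, can add variance and, if the groups differ in how late shock arises, produce a difference where none exists.

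The early-death rule has a separate consequence. It can remove resuscitated infants who die early only when their shock came within a day of admission. Mortality is both a main and a safety outcome, so the rule selects on the outcome, and does so unevenly by onset time. General blood and microbiology results taken at admission may also be out of date for an infant whose shock starts later.

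**Working it through.** **Plan's own figure.** 3 × 30 = 90. No power, effect size or SD is given, so 90 cannot be derived further. From the documents I take only 30 per group, the test rule ("the test was bilateral, and $p < 0.05$ was considered statistically significant") and, as an illustration, the background figure of 40% for mortality. Every other input below is an assumption.

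**1. Early deaths, side by side**

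| | Shock on arrival, death at 20 h | Shock on day 5, death 3 h after resuscitation starts |
|---|---|---|
| Time from admission to death | under 24 h | about 5 days |
| Resuscitated? | yes | yes |
| Counted in mortality? | no | yes |

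Let M be true mortality, s the share in shock at admission, and q the share of deaths within 24 h of shock. Observed mortality = (M − sMq)/(1 − sMq). Take M = 0.40 in both groups, with s = 0.8 v 0.2.
- q = 0.10: (0.40 − 0.032)/(1 − 0.032) = 38.0% v (0.40 − 0.008)/(1 − 0.008) = 39.5%. False difference 1.5 points.
- q = 0.40: (0.40 − 0.128)/(1 − 0.128) = 31.2% v (0.40 − 0.032)/(1 − 0.032) = 38.0%. False difference 6.8 points.
- If s is equal in the groups, there is no false difference from this source.

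**2. Stay, true effect present, equal onset timing.** Assume post-shock stay with median 22 d, log SD 0.5, and a true ratio of 0.70.

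Counted from resuscitation: ln(0.70)/0.5 = −0.713; 0.713/√(2/30) = 2.76; 2.76 − 1.96 = 0.80, so power is about 79% by the normal approximation and about 77–78% by simulated t-test.

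Counted from admission, a hand check at the medians gives the ratio:
- 10% late, 7 d: a late infant's ratio is (15.4 + 7)/(22 + 7) = 0.772; 0.70^0.9 × 0.772^0.1 = 0.71.
- 50% late, 7 d: √(0.70 × 0.772) = 0.735.
- 50% late, 14 d: a late infant's ratio is (15.4 + 14)/(22 + 14) = 0.817; √(0.70 × 0.817) = 0.756.

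Simulation, with pre-shock time exponential (lower power) or lognormal (higher power):

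| Late share, median delay | Ratio | Power |
|---|---|---|
| none | 0.70 | about 78% |
| 10%, 7 d | 0.71 | 73–74% |
| 50%, 7 d | 0.74 | 58–66% |
| 50%, 14 d | 0.76 | 41–51% |

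Power depends on the spread of the delay: with a fixed 14-day delay the last row becomes about 55%.

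**3. Stay, no true effect, unequal onset timing**
- 50% v 40% late: false ratio 1.03 (7 d) to 1.06 (14 d).
- 60% v 30% late: false ratio 1.10–1.11 (7 d) to 1.18–1.19 (14 d), with p < 0.05 in about 12–13% and 21–23% of studies.

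**The case against.** A reader might infer that the plan anchors everything to admission. It does not. No origin is written for either stay outcome or for 28-day survival; admission is only the usual meaning of length of stay. For those outcomes the documented fault is an undefined origin.

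A reader might also infer that severity at baseline is measured at the wrong time. That is mostly answered: lactate, blood pressure and organ support are taken before resuscitation, and nothing restricts the Cox model's baseline covariates to admission values. Only the general blood and microbiology data carry the admission anchor. The age limit at admission is not an error; it merely leaves room for later shock.

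Finally, a reader might infer that onset timing is likely to differ between groups because clinicians choose the monitoring. The documents say nothing on how many infants develop shock after admission, or on whether the choice of monitoring follows onset. If nearly all shock is present on arrival, the anchors almost coincide. If timing is balanced, stay is diluted but not biased.

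All of this stands and limits the size. It does not remove the early-death rule, which is explicit, or the missing origins.

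**Conclusion.** The point holds as a missing common time zero, together with an explicit admission-keyed exclusion that treats early deaths unevenly by shock onset. Followed as written, the plan can drop resuscitated infants from a primary outcome because they died, and leaves the analyst to choose the clock for stay and survival.

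The size is uncertain. With few late-onset cases the loss is minor (about 4 to 5 points of power at 10% late). With half late and long delays, power could fall to between 41% and 51%. A false difference in stay or mortality requires onset timing to differ between groups. Without randomisation that is possible, but the documents do not show it. The 6.8-point mortality figure is the high end, resting on an 80% v 20% split and 40% of deaths falling within 24 h of shock. The issue should be settled before analysis; it does not invalidate the study.

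**What to change.** 1. In Sections 七 and 十, define time zero as the start of the first fluid resuscitation for NICU stay, hospital stay and the 28-day Kaplan-Meier/Cox clock.
2. Add the admission-to-resuscitation interval (or age at shock) to Section 六. Adjust for it in the stay regression and the Cox model, together with the pre-resuscitation values already in item (2).
3. Replace the exclusion based on time from admission, and its application through elimination criterion (1): keep resuscitated infants who die early in the mortality analysis and report early deaths by group. Moving the 24-hour rule to shock onset would make it consistent but would still select on the outcome.
4. Report stay from admission as descriptive only.

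**Cost.** One charted date and time per infant, revised wording in the eligibility and statistical sections, and a small change in which cases enter the analysis. Stay counted from resuscitation will be less directly comparable with ordinary length-of-stay reports, which item 4 partly offsets. No extra patients or procedures are needed.
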